7.6 Special Considerations

Medical and scientific judgment should be exercised in deciding whether expedited reporting is appropriate in other situations, such as important medical events that may not be immediately life-threatening or result in death or hospitalization but may jeopardize the patient or may require intervention to prevent one of the other outcomes listed in the definition above. These should also usually be considered serious. Examples of such events are intensive treatment in an emergency room or at home for allergic bronchospasm; blood dyscrasias or convulsions that do not result in hospitalization; or development of drug dependency or drug abuse or transmission of an infectious agent via a medicinal product.

Serious adverse events occurring after a patient is discontinued from the study will NOT be reported unless the investigator feels that the event may have been caused by the study drug or a protocol procedure. Study-specific clinical outcomes of death because of disease progression are exempt from serious adverse event reporting, unless the investigator deems them related to use of the study drug. Hospitalization for study drug administration is not a serious adverse event.

In general, serious adverse events assessed as clearly being due to disease progression and not due to study drug(s) should be excluded from adverse event reporting. However, in cases where the specificity or severity of an event is not consistent with the risk information, the event should be reported.

7.7 Definition of Reportable Information

In addition to the above events, the following information should be reported to Sanofi Genzyme and the Stanford DSMC:

1. New information that indicates a change to the risks or potential benefits of the research, in terms of severity or frequency.
2. Complaints that are unresolved by the research team, or that indicate increased or unexpected risks.
3. Unanticipated adverse device effect. New information about the effect on health or safety.

7.8 Definition of an Unanticipated Problem

Unanticipated problems involving risks to participants or others (UPs) are events (including internal or external events, death, life-threatening experiences, injuries, breaches of confidentiality, or other problems) that occur any time during or after the research study, which in the opinion of the PD are:

1. Unexpected - not in the consent form, protocol, package insert, or label; or unexpected in its frequency, severity, or specificity, AND

2. Related to the research procedures – caused by, or probably caused by research activity, or, if a device is involved, probably caused by, or associated with the device, AND
3. Harmful – caused harm to participants or others, or placed them at increased risk of harm (including physical, psychological, economic, or social harm).

7.9 Reporting of Pregnancy

If a patient or their partner inadvertently becomes pregnant while on treatment with fresolimumab, the patient will immediately be removed from the study. The site will contact the patient at least monthly and document the patient's status until the pregnancy has been completed or terminated. The outcome of the pregnancy will be reported to Sanofi Genzyme without delay and within 24 hours if the outcome is a serious adverse experience (e.g., death, abortion, congenital anomaly, or other disabling or life-threatening complication to the mother or newborn). If a male patient's partner becomes pregnant on study, the pregnancy must be reported to Sanofi Genzyme. The study investigator will make every effort to obtain permission to follow the outcome of the pregnancy and report the condition of the fetus or newborn to Sanofi Genzyme.

7.10 Definition of an Overdose for This Protocol

Overdose is defined as any dose more than 25% above the prescribed dose described in the study protocol.

7.11 Reporting of Overdose to Sanofi Genzyme

If an adverse experience(s) is associated with ("results from") the overdose of test drug, the adverse experience(s) is reported as a serious adverse experience, even if no other criteria for serious are met.

If a dose of test drug or vaccine meeting the protocol definition of overdose is taken without any associated clinical symptoms or abnormal laboratory results, the overdose is reported as a non-serious Event of Clinical Interest (ECI), using the terminology "accidental or intentional overdose without adverse effect."

All reports of overdose with and without an adverse experience must be reported within 24 hours to Sanofi Genzyme.

7.12 Stopping Rules

Crude rates of grade 3 or higher radiation pneumonitis or bronchopulmonary hemorrhage will be evaluated after 25 patients have finished treatment and completed 6 months of follow up. If a crude rate of >20% is observed, the study will be suspended to evaluate the likelihood of these toxicities being caused by the combination treatment and to decide whether to allow accrual of another test cohort. If a crude rate of $\leq 20\%$ is observed, the study will proceed to primary completion.

All outcome data (toxicity and efficacy) will be reviewed every 6 months by the Principal Investigators and key Co-Investigators. This study will be monitored by the Stanford DSMC. All potential adverse events will be reported to the thoracic disease management group and the DSMC. The study will terminate when the target accrual is met and all data are analyzed.

Comprehensive Safety Review

The rate of NSCLC recurrence will be continuously evaluated for the 1st 10 subjects through 6 months follow-up. In the event that there are ≥ 3 NSCLC recurrences in the first 10 subjects, enrollment will be paused, and a comprehensive safety review will be conducted, which will include the Stanford Cancer Institute Data Safety Monitoring Committee (DSMC). If,

after review, the DSMC recommends proceeding with the study, the report of the safety review will be submitted to the IND, and FDA's concurrence will be sought before proceeding with enrollment.

Similarly, development of new malignancies will be monitored for the first 10 patients through the 6 month follow-up time point [except keratoacanthomas / squamous cell carcinomas (SCC) of the skin]. Keratoacanthomas and SCC are not included because these are known events that regress after discontinuation of fresolimumab therapy, per the Investigator's Brochure. These lesions will be referred to a dermatologic oncologist or dermatologist for evaluation, treatment, and monitoring, but will not be tabulated towards the criteria for enrollment pause. New malignancies are expected to be rare, and if more than 2 subjects develop new malignancies, enrollment would be similarly paused for a comprehensive safety review as above.

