2.4 Study Design

Phase 1 component:

Fresolimumab will be on Days 1, 15, and 36 and SABR will be administered at 12.5 Gy/fraction in 4 fractions between Days 8 and 12 to a total of 5 patients who will be evaluated for safety, and additional patients will be enrolled if specific AE's are observed. A dose reduction may be implemented if excessive toxicity is observed.

Blood would be collected for pharmacokinetic studies (only Phase 1). This is a single-arm, open-label study

Phase 2 component:

Up to a total of 60 patients, including the Phase 1 portion. Fresolimumab will be administered IV at the dose selected in the preceding Phase 1 (3 mg/Kg) component on Days 1, 15 (+ 6 days), and 36 (+/- 6 days) and SABR (-1/+5 days) will be administered at 12.5 Gy/fraction in 4 fractions between Days 8 and 12.

This is a single-arm, open-label study conducted under IND 125981 (Sponsor-Investigator/ IND Holder: [name], PhD).

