12.5 Sample Size

12.5.1 Accrual Estimates

Number of Patients: 55 to 60

In 2014, ~80 lung SABR procedures were performed at Stanford Hospital. It is estimated that 2 to 3 patients can reasonably be expected to accrue per month. Accrual will occur over 60 months.

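### Section 7.12 reads its toxicity criterion once, and nothing written requires action when a sixth event among the 25 patients has already decided the result

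*Combined protocol and SAP*

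**What the plan says.** Section 7.12 (Stopping Rules) tracks "Crude rates of grade 3 or higher radiation pneumonitis or bronchopulmonary hemorrhage". The rate "will be evaluated after 25 patients have finished treatment and completed 6 months of follow up". The consequence is: "If a crude rate of >20% is observed, the study will be suspended to evaluate the likelihood of these toxicities" and to decide on further accrual. At or below 20%, the text ends with "is observed, the study will proceed to primary completion". One reading is described. There is no running count, no earlier trigger, and no hold on accrual while the 25 patients complete follow-up. The section does not label this a phase 2 rule or say whether phase 1 patients count among the 25.

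Other oversight exists. Sections 7.12 and 12.2 call for six-monthly reviews of outcome and safety data. The data and safety monitoring committee (DSMC) monitors the study (7.12) and regularly reviews serious adverse events (11.2). Section 7.5 requires those events to reach the DSMC within 2 working days. None of these provisions refers to the 20% limit or to a number of events.

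On accrual, Section 12.5.1 says "It is estimated that 2 to 3 patients can reasonably be expected to accrue per month", and also "Accrual will occur over 60 months". Section 2.4 sets the ceiling: "Up to a total of 60 patients, including the Phase 1 portion".

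**The concern.** A proportion with a fixed denominator of 25 can be decided before all 25 patients have been observed. Events already counted are not undone by later patients, so waiting for the look adds nothing to this particular decision once the sixth event has occurred. Meanwhile the protocol as written leaves enrolment open, so more patients may start a combination that has already exceeded the sponsor's own limit.

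The protocol handles comparable rules differently. In the same section, cancer recurrence is assessed continuously in the first 10 subjects and enrolment pauses at the third recurrence. New malignancies in those subjects are also monitored, with a pause. The phase 1 rule in Section 4.2.1 can act before its first cohort of 5 is full. The criterion in 7.12, which counts the same two toxicities as the phase 1 rule, is the one that waits for its full group.

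**Working it through.** **Inputs from the documents.** The single look, the 25 patients and the 20% limit come from Section 7.12. Accrual of 2 to 3 per month, 55 to 60 patients and 60 months come from 12.5.1; the last two imply 55/60 = 0.92 to 60/60 = 1 per month. Follow-up visits are counted from the end of SABR, about Day 12 (Section 9). The last fresolimumab dose is on Day 36. Grade 3 or higher pneumonitis is expected in at most 10% (12.5.2).

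**Assumptions, not in the documents.** True rates of 10% to 30%. Event onset uniform over 0.5 to 3.5 months or over 1 to 6 months after entry.

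The plan gives no event count or error rate for this rule, so there is no stated figure to reproduce.

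**1. Boundary.** 5/25 = 20.0%, which is not above 20%. 6/25 = 24.0%, which is. The rule is 6 or more of 25.

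**2. Chance that the rule is met.** With X binomial (25, p), P(X ≥ 6) is:

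| True rate p | P(X ≥ 6) |
|---|---|
| 10% | 3.3% |
| 20% | 38.3% |
| 30% | 80.7% |

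**3. Enrolment by the look.** From entry of the 25th patient to the look takes 6 + 12/30.4 = 6.4 months if follow-up runs from the end of SABR, or 6 + 36/30.4 = 7.2 months if it runs from the last dose. With the shorter clock, the number enrolled is 25 + rate × 6.4:
- 1 per month: 25 + 6.4, about 31
- 2 per month: 25 + 12.8, about 38
- 3 per month: 25 + 19.2, about 44

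**4. Lag from the sixth event to the look.** This was simulated with Poisson accrual and the shorter clock, keeping only trials with six or more events among the first 25 and assuming that nobody acts before the look. Medians at a true rate of 30%, with ranges over the two onset assumptions:

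| Accrual per month | Lag (months) | Further patients enrolled |
|---|---|---|
| 1 | 9.9 to 11.4 | 10 to 12 |
| 2 | 6.4 to 7.9 | 13 to 16 |
| 3 | 5.2 to 6.7 | 16 to 20 |

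At a true rate of 20%, the shortest median lag is about 4 months (3 per month, later onset) and the smallest median number of further patients is about 7 (1 per month, later onset). Across true rates of 20% to 30% and accrual of 1 to 3 per month, the ranges are about 4 to 11 months and about 7 to 21 patients.

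A separate run used evenly spaced accrual, the 7.2-month clock, true rates of 20% to 40%, and onset at 1 to 6 or 0.25 to 2.2 months. It gave mean lags of 5.2 to 17.3 months and 8 to 28 further patients.

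**5. If the 25 are completers only.** Suppose a fraction q of patients with an event leave before 6 months, and patients without an event do not. The event rate among completers is 0.30(1 − q) / [0.30(1 − q) + 0.70].
- q = 1/6: 0.25/0.95 = 26.3%, so P(X ≥ 6) = 68%
- q = 1/4: 0.225/0.925 = 24.3%, so P(X ≥ 6) = 59%

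Both compare with 81% when all 25 treated patients are counted.

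**The case against.** The strongest objection concerns who the 25 are. Read literally, Section 7.12 evaluates patients who completed 6 months. A patient who has an event and then dies or withdraws may not be among them. A reader might infer that any six events among treated patients make suspension certain, and that acting on them changes nothing but timing. The documents do not support that: six events among treated patients can leave five or fewer among 25 completers, and step 5 shows that the difference can be material. The point holds only for events among the patients finally evaluated. This objection stands, so the 25 must be defined.

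Second, a reader might infer that enrolment would certainly continue past the sixth event. That is also too strong, because it rests on silence. The DSMC would see serious events quickly. At a 30% rate and 2 to 3 patients per month, a six-monthly review with random timing would fall inside the lag in about 80% to 96% of trials that meet the rule. Such a review could lead to action, but nothing requires it. What stands is that the patient counts above assume no discretionary action.

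Third, the gain depends on toxicity being high. At the expected pneumonitis rate of at most 10%, the criterion is rarely met, and the saving averaged over all trials is about 0.3 to 0.5 patients at 2 to 3 per month. That is correct, but high toxicity is the case for which the rule exists.

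Finally, a single look is a coherent design, and phase 1 screens for the same toxicities first, though over a shorter window. Neither gives a reason to wait once the result is fixed.

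**Conclusion.** The concern holds in a limited form. The criterion is read once. Six events among the patients who make up the 25 decide it, and no written provision requires action before the look.

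The lag and patient counts in step 4 are conditional on the rule being met and on nobody acting earlier. They also rest on onset times and true rates that the documents do not give. At the slower accrual implied by 60 patients in 60 months, only about half of the trial is enrolled at the look, so it would be wrong to conclude that most of the trial is always exposed by then.

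The change is worth making because it applies the sponsor's own limit when it is met, as the recurrence rule in the same section already does.

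**What to change.** Keep the qualifying events and the limit of more than 20% of 25. Add to Section 7.12:

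- The 25 are the first 25 treated patients. Those with a qualifying event who die or leave before 6 months are counted. State whether phase 1 patients are included.
- The existing suspension and review take place as soon as the sixth qualifying event occurs among those 25, and otherwise at the planned look.
- The existing six-monthly safety review reports the running count.

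With the 25 so defined, the probability of suspension equals that of a single look at the same patients, and only the timing changes. No extra patients or assessments are needed, and the reporting channels already exist.

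The cost is a few sentences. If the sponsor meant completers only, fixing the denominator raises the chance of suspension somewhat. The rise is small if few patients with events leave early, and larger under the losses assumed in step 5.

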7.13 Confidentiality

Study data will be maintained in protected patient binders. Only research personnel listed on this protocol will have access to this information. Only the patients unique IDN will be used. Specimens will be stored under the patient's IDN.

8. CORRELATIVE/SPECIAL STUDIES

8.1 Pharmacokinetic Analyses

Serum samples will be collected before and within 4 hours post each dose of fresolimumab for PK studies. Instructions for collection are as follows:

Group Name(s)	Container(s)	Collection Instructions
SM/ GC1008 Pre-infusion PK	1- 5mL gold top serum separation tube 1- 7mL clear cryovial	One 5mL gold top serum separation tube. Collect 5mL blood into the Serum Separator tube. Fill tube completely. It is important to thoroughly mix the blood with the clotting activation agent by inverting the tube not less than five times. Allow blood to clot for 30 minutes (tube standing upright). Use pipette provided to transfer all of the serum into the appropriately labeled tubes. Freeze immediately at -70°C until shipment. Keep all samples frozen until ready to ship. Ship frozen to Covance CLS Day of Collection
SM/ GC1008 Post-infusion PK	1- 5mL gold top serum separation tube per timepoint 1- 7mL clear cryovial per timepoint	One 5mL gold top serum separation tube. Collect 5mL blood into the Serum Separator tube. Fill tube completely. It is important to thoroughly mix the blood with the clotting activation agent by inverting the tube not less than five times. Allow blood to clot for 30 minutes (tube standing upright). Use pipette provided to transfer all of the serum into the appropriately labeled tube. Freeze immediately at -70°C until shipment. Keep all samples frozen until ready to ship. Ship frozen to Covance CLS Day of Collection

8.2 Coding of specimens for privacy protection

At the time of enrollment each patient will be given a specific confidential identification number (IDN). Specimens will be stored under the patient's IDN. The information can be shared with other investigators listed on this protocol. Study data will be maintained in password protected

computer files (protected online database). Only research personnel will have access to this information.

9. STUDY CALENDAR

Parameters	Pre-Entry ⁶	Day 1	Day 8-12 ⁴	Day 15 ⁷	Day 36 ⁸	3 month ^{9,10}	6 month ¹⁰	9 month ¹⁰	12 month ¹⁰
History & Physical Exam	X	X		X	X	X	X	X	X
Complete skin exam ¹	X					X			
ECOG PS	X	X		X	X	X	X	X	X
Labs ²	X	X		X	X	X	X	X	X
CT Thorax (Chest)	X ¹¹					X	X	X	X
PET/CT	X ¹¹						X		
Toxicity evaluation		X		X	X	X	X	X	X
PFT ³	X						X		X
SABR ⁴			X						
Fresolimumab ⁵		X		X	X				

- ¹ To be performed by the investigators. Suspect lesions will be referred for further evaluation to a dermatologic oncologist or dermatologist as appropriate
- ² Includes CBC with differential and complete metabolic panel. Also urine or serum pregnancy test required for women of childbearing potential at pre-entry only
- ³ Including DLCO, FEV1, and FVC
- ⁴ 12.5 Gy/fraction in 4 fractions between Days 8 to 12. Minus 1 to + up to 5 days to allow for weekends and holidays and unforeseen circumstances.
- ⁵ 3 mg/kg IV (or other determined dose from Phase 1) given on days 1, 15, and 36
- ⁶ All pre-entry assessment should be obtained within 4 weeks of enrollment
- ⁷ 3 days after completion of SABR, + up to 6 more days to allow for weekends and holidays and unforeseen circumstances
- ⁸ Target 21 days after dose 2 of fresolimumab. +/- 6 days to allow for weekends and holidays and unforeseen circumstances
- ⁹ Needs to be at least 90 days after completion of SABR for safety analysis
- ¹⁰ +/- 2 weeks to allow for weekends and holidays and unforeseen circumstances. Date counted from completion of SABR.
- ¹¹ Acceptable to use non-diagnostic simulation planning scans for baseline imaging

10. MEASUREMENT OF ENDPOINT

10.1 Scoring of post-SABR radiologic changes

The extent of SABR-induced radiologic changes will be scored at each follow-up scan. Scoring of radiologic changes will be performed by at least two radiologists or radiation oncologists dedicated to the study, who will be blinded to the treatments the patients receive. Scores will be assigned by consensus.

Assessment of fibrosis will be performed based on three previously-published scales by Dahele, *et al.* [15] In the phase 2 component of the study, the severity score of fibrosis in study subjects will be compared to historical controls. Historical controls will consist of patients previously-treated with the same dose of SABR (50 Gy in four fractions) at Stanford in the absence of fresolimumab.

Late Radiation Fibrosis Score (Pattern):

Late CT changes will be defined as occurring at 12 months after enrollment and will consist of:

- 1) "Modified conventional pattern" of fibrosis characterized by consolidation, volume loss, and bronchiectasis with or without GGO,
- 2) Mass-like fibrosis characterized by a well-circumscribed focal consolidation limited to the tumor region but which is larger than the original tumor,
- 3) "Scar-like fibrosis" consisting of a linear opacity in the tumor region with associated volume loss, or
- 4) "No evidence of increasing density" including stable or regressing mass at the location of the treated tumor with no or minimal GGO or only normal appearing lung tissue.

Acute Radiation Fibrosis Score (Pattern):

The categories of acute findings (occurring in the first 6 months after enrollment) will be:

- 1) Diffuse consolidation,
- 2) Patchy consolidation,
- 3) Diffuse ground-glass opacities (GGOs),
- 4) Patchy GGO, or
- 5) No evidence of increasing density. The term "diffuse" will apply to abnormalities that are at least 5 cm in maximum diameter and which contain more than 50% abnormal lung. Abnormalities not meeting these criteria will be termed "patchy".

Severity Score:

We will assign an overall severity score of radiographic fibrosis at 6 and 12 months after enrollment using the categories:

- 1) "Severe" (much more extensive than usually seen after SABR),
- 2) "Moderate" (changes that are commonly seen after SABR),
- 3) "Mild"/"minor" (unusually slight changes compared to what is normally observed after SABR), or
- 4) "None."

"Presence of moderate-to-severe fibrosis" at 12 months will be defined as severity fibrosis scores 1 or 2 (ie, "Severe" or "Moderate") . This will serve as the primary endpoint for Phase 2.

Pattern and severity of fibrosis at 6 months and pattern of fibrosis at 12 months will be evaluated as secondary endpoints for both Phase 1 and 2 of the study.

Patients who are lost to follow-up and who do not have a scan within +/-6 months of the 12-month time point will be excluded from analysis. Patients who develop inflammatory lung conditions unrelated to radiotherapy (i.e. pneumonia, ARDS, drug-induced pneumonitis, etc.)

will be excluded from the final endpoint analysis if the area of unrelated inflammation impedes scoring of fibrosis severity of the irradiated lesion.

Quantitative image analyses:

Finally, we will explore quantitative image analysis metrics for evaluating radiation fibrosis. This will include analyses such as contouring the region of fibrosis and quantifying its volume relative to the total lung volume and/or the original dose distribution. Similarly, FDG-uptake metrics will be examined on the follow-up PET/CT.

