4.2.3 Duration of Therapy

Patients will be seen on Days 1, 15, and 36 when they receive fresolimumab, and will be seen in follow-up at 3rd; 6th; 9th and 12th month from end of SABR completion (+/- 2 weeks). History and physical exam, ECOG PS, toxicity evaluation, CT Thorax (Chest) imaging, and labs will be evaluated at each of these visits. Skin exams will be conducted at the 3rd month from end of SABR completion. PFTs will be completed at 6th and 12th month. PET/CT imaging will be evaluated at 6th month. The duration of the treatment phase of the study will be through the 1st follow-up visit, approximately 90 days after the SABR is completed.

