4.2.4 Duration of Follow-Up

The follow-up portion of the study will begin approximately 90 days after SABR is completed through 12 months from enrollment. Further follow-up information is on the study calendar.

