12.4 Primary and Secondary Endpoints

Phase 1:

Primary Endpoint

- Dose limiting toxicities (DLTs) of fresolimumab when combined with SABR

Secondary Endpoint

- Score the pattern of late radiation induced fibrosis at 12 months after SABR with and without fresolimumab
- Evaluate severity and pattern of acute radiation-induced fibrosis in the first 6 months after SABR
- Score potential adverse events (AEs) of fresolimumab combined with SABR using CTCAE v4
- Measure post-treatment changes in pulmonary function using pulmonary function test parameters at enrollment, 6-month, and 12-month follow-up
- Evaluate recurrence and progression-free survival at 12 months
- Measure blood pharmacokinetics (PK) of fresolimumab in combination with SABR (optional for patient)

Exploratory Endpoint:

- Assess extent of radiation-induced lung toxicity by quantitative imaging analysis of CT volumes and FDG uptake parameters

Phase 2

Primary Endpoint

Evaluate the presence of late moderate-to-severe radiation-induced fibrosis up to 12 months after SABR with fresolimumab

Secondary Endpoint

- Score the pattern of late radiation induced fibrosis at 12 months after SABR with and without fresolimumab
- Evaluate severity and pattern of acute radiation-induced fibrosis in the first 6 months after SABR
- Score potential adverse events (AEs) of fresolimumab combined with SABR using CTCAE v4
- Measure post-treatment changes in pulmonary function using pulmonary function test parameters at enrollment, 6-month, and 12-month follow-up
- Evaluate recurrence and progression-free survival at 12 months

Exploratory Endpoint:

- Assess extent of radiation-induced lung toxicity by quantitative imaging analysis of CT volumes and FDG uptake parameters

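### Imaging time points run from enrollment in 10.1 and 4.2.4 but from SABR completion elsewhere; because recurrence and PFS also run from enrollment, most events first seen on the 12-month CT fall after the 12-month landmark

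*Combined protocol and SAP*

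**What the plan says.** Two time origins stand in the current text.

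**Counted from enrollment**
- Section 10.1, acute pattern: "occurring in the first 6 months after enrollment".
- Section 10.1, late pattern: "Late CT changes will be defined as occurring at 12 months after enrollment".
- Section 10.1, severity: an "overall severity score of radiographic fibrosis at 6 and 12 months after enrollment". The 12-month score supplies the Phase 2 primary endpoint.
- Section 4.2.4: follow-up runs "through 12 months from enrollment".
- Section 10.2: recurrence and PFS run from enrollment to the first documented date of the event.

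**Counted from SABR**
- Section 4.2.3: visits and chest CTs at 3, 6, 9 and 12 months after the end of SABR, +/-2 weeks.
- Section 9, calendar footnote 10: "Date counted from completion of SABR".
- Synopsis and Section 12.4: "acute radiation-induced fibrosis in the first 6 months after SABR", with the Phase 2 primary endpoint also counted from SABR.

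**Origin not stated**
- Sections 10.1 and 12.4.1 accept a scan within +/-6 months of the 12-month time point.
- Section 12.4.2 reads Kaplan-Meier estimates at multiples of 12 months and estimates local control at 12 months.

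**The concern.** SABR is always completed after Day 1, so a scan timed from SABR falls later on an enrollment clock than its nominal month. An offset of one to a few weeks is short against the course of fibrosis, but it moves scheduled scans across fixed cut-offs.

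For fibrosis, the scoring section and the endpoint list give different clocks for the same endpoint. For recurrence and PFS the effect is on the estimate itself. The event date is the date of documentation, the scheduled CT is the main means of detection, and the last scheduled CT usually falls just after the landmark at which the estimate is read. Events first seen on that CT then drop out of the 12-month figure, which favours the treatment.

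**Working it through.** The plan gives no figure for this offset, so there is none to reproduce.

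**Inputs**
- SABR: Days 8 to 12, -1/+5 days (Section 4.2.1, calendar footnote 4). Latest completion is 12 + 5 = Day 17. Earliest is taken as Day 10, assuming four consecutive daily fractions from Day 7.
- Scan window: +/-14 days, or 29 allowed days (Section 4.2.3, footnote 10).
- Gap *g* from enrollment to Day 1: not stated. Footnote 6 ties only the pre-entry assessments to enrollment. Range shown: 0 to 28 days.
- Scans spread evenly over the allowed days (assumed).

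**Step 1: offset**

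With SABR completed on Day *c*, the on-target 6- or 12-month scan falls *g* + (*c* - 1) days after the same mark counted from enrollment. The share past the mark is the number of allowed days beyond it, divided by 29.

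| *g* | *c* | Target offset (days) | Allowed range (days) | Share past the mark |
|---|---|---|---|---|
| 0 | 10 | 9 | -5 to +23 | 23/29 = 79% |
| 0 | 11 | 10 | -4 to +24 | 24/29 = 83% |
| 0 | 12 | 11 | -3 to +25 | 25/29 = 86% |
| 0 | 17 | 16 | +2 to +30 | 29/29 = 100% |
| 7 | 10 | 16 | +2 to +30 | 100% |
| 28 | 10 to 17 | 37 to 44 | +23 to +58 | 100% |

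An on-target scan is always past the mark. With *g* = 0 and SABR ending on Days 10 to 12, a scan meets the enrollment-based limit only if done at least 9 to 11 days early. With SABR ending on Day 17, or with *g* of 7 or more, no allowed scan meets it.

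**Step 2: fibrosis endpoints**

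The largest target offset, 44 days, is far inside the +/-6-month allowance, and so is the latest allowed scan (+58 days). No on-schedule 12-month scan leaves the primary analysis. Section 10.1 separately names pattern and severity at 6 months as secondary endpoints, so the 6-month scan is still scored.

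**Step 3: 12-month recurrence and PFS**

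For illustration, assume a constant hazard, detection only at scheduled scans, and every 12-month scan past the mark. The 12-month estimate then holds only events detected through the 9-month scan. If the true 12-month event rate is F, it reads 1 - (1 - F)^(9/12):

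- F = 10%: 1 - 0.90^0.75 = 7.6%
- F = 20%: 1 - 0.80^0.75 = 15.4%
- F = 30%: 1 - 0.70^0.75 = 23.5%

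True local control of 80%, the benchmark in Section 12.4.2, would read 0.80^0.75 = 84.6%, if local control is also timed from enrollment.

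Two refinements for F = 20%:
- The 9-month scan is itself 9 to 16 days late, so exposure is (273.75 + 9)/365 = 0.775 to (273.75 + 16)/365 = 0.794 of a year. The reading becomes 15.9% to 16.2%.
- With *g* = 0 and *c* = 10, 6/29 = 21% of 12-month scans fall on or before the mark. The reading is then roughly 15.9 + 0.21 x (20 - 15.9) = 16.8%.

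The shortfall at a true 20% is therefore about 3 to 5 percentage points.

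**Step 4: is a common origin enough?**

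Counted from SABR, the target offset is 0, but the allowed days still run from -14 to +14, and 14/29 = 48% lie after a strict cut-off. The visit window must also be included in the landmark.

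**The case against.** The intended clock for fibrosis can be recovered. The endpoint lists and the calendar both use SABR, and Section 4.2.4 itself refers the reader to the calendar for further follow-up detail. That stands, and it rules out three stronger readings.

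- A reader might infer that the 6-month scan drops out and the acute endpoint rests on the 3-month scan alone. Section 10.1 has changes scored at every follow-up scan and lists 6-month pattern and severity as endpoints. The loss appears only if one parenthesis overrides both.
- A reader might infer that follow-up closes before the 12-month CT, so the primary endpoint is not collected. Nothing in Section 4.2.4 cancels the scheduled visit or excludes its data, and the +/-6-month rule keeps the scan.
- A reader might take the bias in PFS and recurrence as established at a given size. Events found at 3, 6 or 9 months, or between visits, count either way. Only those first seen on the 12-month CT are at risk, and the sizes above are illustrative.

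It is also fair to say that a landmark placed on a visit date causes trouble under any origin, as the 48% in step 4 shows. That does not remove the point: the enrollment clock raises 48% to between 79% and 100%. Nor does the inference that rescues fibrosis help here, because Section 10.2 fixes enrollment as the origin for recurrence and PFS.

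**Conclusion.** The point holds in two parts of unequal weight.

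For fibrosis it is a contradiction to reconcile, with no scan lost, the Phase 2 primary endpoint essentially unaffected, and sample size unchanged.

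For 12-month recurrence and PFS, and for local control if timed from enrollment, it matters more. Followed exactly, the plan omits most events first detected on the last scheduled CT, and the error is in the favourable direction. The 79% to 100% of allowed scan days past the mark rests on enrollment on Day 1, SABR ending on Days 10 to 17, and evenly spread scans. With an assumed gap of 7 days or more before Day 1, it is 100%. The drop from a true 20% to about 15% rests on constant hazard, detection only at scheduled scans, and all 12-month scans past the mark. Interim detection or earlier scans would shrink it.

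**What to change.** - In Sections 10.1 and 4.2.4, count the imaging time points and the end of follow-up from SABR completion, and state that origin for the +/-6-month rule in Sections 10.1 and 12.4.1.
- Define acute findings by the scheduled 3- and 6-month scans and late findings by the scheduled 12-month scan, each with its visit window.
- In Sections 10.2 and 12.4.2, set the 12-month landmark to include the 12-month visit and its window, or assign each event to the scheduled visit at which it was found. State the origin for local control as well.

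Make the change before scoring and analysis, so that windows are not chosen with results in view.

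The cost is wording only, with no added scan or visit. The stated landmark will be slightly later than 12 months from enrollment, and the estimates may become slightly less favourable.
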